**PART II**  
**RESEARCH PROPOSAL**

**1. SPECIFIC AIMS.**

**Problem Statement:** Loss of supraspinal control of autonomic pathways interrupts homeostasis of multiple organ systems including thermoregulation. Thermoregulatory mechanisms are dysfunctional due to interrupted sympathetic pathways for hypothalamic control of vasomotor and sudomotor function and motor/sensory pathways for shivering and thermal sensation. During exposure to warm seasonal temperatures, dysregulation of heat dissipating mechanisms (vasodilation and sweating) allows core body temperature (Tcore) to rise in persons with SCI rather than remaining stable and tightly regulated ( $\sim 37 \pm 0.6^\circ\text{C}$ ), as occurs in able-bodied (AB) persons. We have reported in persons with higher lesions (SCI > T6: Hi-SCI), that even limited exposure (1-2 hours) to typical summer temperatures (35°C) can result in Tcore rising to values approaching hyperthermia ( $\geq 38^\circ\text{C}$ ). Mild hyperthermia causes physical discomfort and can impair cognition. Unchecked, hyperthermia can progress to heat exhaustion and heat stroke causing seizures, loss of consciousness, and potentially death, as occurred in vulnerable residents of the Pacific Northwest during a heat wave in late June 2021.

Current medical advice for those with SCI is to avoid direct sunlight, dress sparingly, drink plenty of fluids, and stay indoors on hot, humid days. Despite heeding this advice, persons with SCI frequently find themselves in hot environments for prolonged periods during social, religious, or work functions. During these conditions, there is rapid progression to feeling “overheated” and an increased risk for heat-related illness. Warm seasonal temperatures limit perceived comfort, performance of activities, and participation in societal functions to a greater extent in persons with cervical injury (tetraplegia) than in AB controls. Identifying a safe, non-invasive, efficacious bioengineering intervention to restore thermoregulatory function during heat exposure has the potential to minimize the negative impact of heat on activities, participation, and quality of life (QOL) in Veterans with SCI. If efficacious, other Veteran populations adversely affected by heat exposure may also benefit from this intervention.

**Secondary Objective (Efficacy in SCI):** To determine the efficacy of the wet cooling vest to maintain Tcore (within 0.3°C) in participants with Hi-SCI when exposed to 2 hours of a warm environment. Using a repeated measures design, participants with Hi-SCI will wear the wet vest (experimental condition) or no vest (control condition) in a warm thermal chamber (35°C) for up to 2 hours in the seated position, to determine: (1) change in Tcore and (2) perception of heat and thermal comfort.

**Secondary Hypotheses:** In our previous investigation of heat exposure, 65% of persons with Hi-SCI had increases of  $> 0.5^\circ\text{C}$  in Tcore (mean increase  $0.6 \pm 0.3^\circ\text{C}$ ) while wearing only shorts. We expect that

wearing a cooling vest during the same heat exposure, will significantly increase heat dissipation and, thus, enhance maintenance of Tcore and thermal comfort. We hypothesize that during a controlled warm exposure (35°C), participants with Hi-SCI wearing the wet cooling vest compared to the same participants not wearing a vest: 1) 65% will have a significantly reduced elevation in Tcore ( $\leq 0.3^{\circ}\text{C}$ ), and 2) a greater percentage of participants will report increased thermal comfort (decreased perception of feeling “hot”, “very hot”, or “uncomfortable”).

## 2. BRIEF REVIEW OF RESULTS OF OTHERS AND CURRENT STATE OF KNOWLEDGE

### Background

The interruption of autonomic pathways after spinal cord injury (SCI) causes dysregulation of multiple organ systems, including thermoregulation. The consequences of an impaired ability to maintain core body temperature (Tcore) may be more subtle than the limitations in activities and mobility caused by muscle paralysis due to interrupted motor pathways. Thermoregulation negatively impacts health, personal comfort, and the willingness to participate in functions outside the home. The prevalence of thermoregulation in persons with SCI has not been reported, but it is related to the integrity of sympathetic pathways for vasomotor and sudomotor function and motor/sensory neurological level of injury (NLI) for shivering and sensation. The ability to redistribute blood between central and peripheral compartments is impaired the most in persons with tetraplegia (NLI  $\geq \text{C8}$ ) and high paraplegia (NLI  $\geq \text{T6}$ ) due to dysfunctional vasomotor control of central (splanchnic) and peripheral (lower extremity) vascular beds, resulting in orthostatic hypotension, as well as autonomic dysreflexia due to vascular dysregulation.

### Thermoregulation in Warm Conditions in Able-Bodied (AB) Persons

Thermoregulation is a precisely controlled homeostatic function, which maintains Tcore within a narrow range ( $37.0 \pm 0.6^{\circ}\text{C}$ ) despite a wide range of environmental temperature challenges. Effective thermoregulation depends on the integrity of afferent thermal sensory information, from cutaneous and deep thermal receptors, for cortical awareness and initiation of biobehavioral responses (i.e., add or remove clothing) and for preoptic hypothalamic processing for appropriate modulation of efferent thermoregulatory responses. Upon recognition of excessive heat storage, from either warm ambient conditions or physical activity, the hypothalamus rapidly orchestrates sympathetic-mediated responses of vasodilation and sweating to dissipate heat to maintain Tcore within the range of normothermia as well as perceived thermal comfort.

### Thermoregulation in Warm Conditions after SCI

In persons with SCI, the interruption of sympathetic pathways limits central regulation of vasodilation and sweating for increasing heat loss and vasoconstriction for decreasing heat loss. Motor pathway interruption, identified by the International Standards for Neurological Classification of Spinal Cord Injury (ISNCSCI), limits involuntary shivering for thermogenesis, as well as the ability to move to more temperate environments. Interruption of sensory pathways, also identified by the ISNCSCI, impairs awareness of warm or cool ambient conditions, delaying biobehavioral responses (i.e., adding or removing clothing) and the ability of the hypothalamus to rapidly orchestrate an effective response. As a result, Tcore varies directly with ambient conditions and is frequently outside the optimal range of normothermia. This dysfunction is more prevalent in persons with SCI above T6 (Hi-SCI) because control of vasomotor and sudomotor function has been de-centralized in greater than 60% of the body's surface area and the availability of skeletal muscle for shivering and mobility is limited due to paralysis below the neurologic level of lesion (NLI). When in warmer environments or during warmer seasons, the limited ability to dissipate heat from ambient temperature exposure or generated by physical activity results in a predominantly unregulated rise in Tcore and an increased vulnerability to hyperthermia (Tcore  $\geq 38^{\circ}\text{C}$ ). Hyperthermia can affect central nervous system function, causing impaired cognitive performance, consciousness, blurry vision, nausea, and dizziness. If unchecked, hyperthermia can lead to heat stroke, causing loss of consciousness, permanent central nervous system damage, and progress to multiple organ system failure and death. From 2004 to 2018, a total of 10,527 deaths in the United States resulted from heat exposure. The dangers of

prolonged heat exposure in vulnerable persons were demonstrated by a heat wave that occurred in June 2021 in the Pacific Northwest.

Dysfunctional thermoregulation after SCI also affects quality of life (QOL). Heinemann et al. assessed the influence of environmental factors that were perceived as barriers and affected health-related QOL in persons disabled from neurological injuries; 570 participants who suffered a stroke, traumatic brain injury (TBI), or SCI (SCI: n=193) rated the difficulty of 18 perceived barriers in home, outdoor, and community settings. “Feeling too hot or cold outdoors” was the *most* frequently reported barrier of the 18 items, while “feeling hot or cold at home” was the fourth most common barrier. “Feeling too hot or cold in stores” was eighth most common barrier.

When participating in social, religious, or work functions during warmer seasons, persons with SCI frequently find themselves in hot environments for prolonged periods, rapidly progressing from feeling comfortably warm to feeling “overheated” and uncomfortable and at increased risk for heat-related illness. However, interventions addressing thermoregulation during heat exposure in persons with SCI are limited. Exploration of a safe, efficacious bioengineering intervention that has the potential to minimize the adverse effects of prolonged heat exposure and its negative impact on participation and QOL in Veterans with SCI should be a priority. If efficacious, other vulnerable Veteran populations adversely affected by heat exposure, e.g., persons with 3rd degree burns, MS, and aged  $\geq 70$  years of age, may also benefit from this intervention,

### **Cooling Interventions to Decrease the Risk of Hyperthermia in Able-Bodied (AB) Persons**

Studies in athletes to reduce heat-related illness, increase performance, and control the rise in Tcore during exercise in warm ambient conditions have utilized cooling vests, cold water immersion, ice slurry ingestion, cooling packs, and facial wind and water sprays. Investigators have used cooling prior to heat exposure (pre-cooling) to increase heat storage capacity and/or during heat exposure (per-cooling) to limit heat accumulation. The cooling vest was found to be most effective during per-cooling due to its ability to cover a large surface area of the body and its practicality. Combining its use to both before and during exercise afforded the greatest cooling effect.

### **Cooling Interventions to Decrease the Risk of Hyperthermia in Persons with SCI**

Cooling interventions explored in persons with SCI have included hand and foot cooling, water sprays (spray-bottles), and cooling garments (vests, hats, neckbands) primarily during exercise conditions and with varying results. An aluminum back plate on a wheelchair cooled by Peltier transformers was developed, but only tested in 5 AB subjects during heat exposure. The most promising of these interventions seems to be the ice vest and water spray on exposed skin, which, when used either before or during exercise in persons with tetraplegia, resulted in Tcore being significantly lower compared to the control condition (exercise with no vest or no water spray). Bongers et al. studied use of a cooling vest in persons with low paraplegia during exercise in temperate ambient conditions. They found that the vest improved comfort, lowered skin temperatures, and improved core/skin thermal gradient, but did not prevent the increase in Tcore. However, persons with low paraplegia have greater thermoregulatory capacity than those with Hi-SCI and the vest may have had a greater effect in persons with Hi-SCI during warmer conditions (greater heat load), as evidenced by Trbovich et al. using water spray. Webborn et al. compared the use of an ice vest in athletes with tetraplegia during exercise in warm conditions; the vest, either before (20 minutes prior) or during exercise, attenuated the rise in Tcore and improved comfort compared to exercise with no vest.

However, when used outdoors and for longer periods (e.g., outdoor summer travel, social events), there are disadvantages of using a passive ice vest (i.e., replenishing the ice in the vest and the necessity of carrying ice). Similar disadvantages exist with water spray (i.e., having someone assist with spraying and replenishing the water for the spray). The feedback-controlled “smart” cooling vest does not need refilling because it continually cools and recirculates the cooled water for improved heat conduction, its temperature can be controlled, and once wet, the material of the vest will continue to provide evaporative heat loss for 3-4 hours.

## **3. PROCEDURES, METHODS AND EXPERIMENTAL DESIGN.**

**Research Design:** An exploratory protocol with two phases (AB safety; SCI safety and efficacy) will be performed. In Phase 1, because those with Hi-SCI potentially have impaired or absent skin temperature sensation, AB participants will wear the wet “smart” cooling vest to determine its safety. Phase 2 will be performed for efficacy in a single group of persons with Hi-SCI in a prospective, repeated measures design with two conditions (experimental: *wet vest*, control: *no vest*) administered in random order. The objective of Phase 2 is to determine if persons with Hi-SCI dissipate body heat more effectively in the *wet vest* condition compared to the *no vest* condition as evidenced by a smaller rise in Tcore, a decreased perception of heat, and increased thermal comfort. We expect a mean increase in Tcore of  $0.6 \pm 0.3^{\circ}\text{C}$  and a perception of feeling “hot or very hot” in the *no vest* condition, as evidenced in two of our prior studies with identical challenges.

**Participants:** Ten participants with high-level SCI (C4-T2, AIS A & B) and 5 AB participants matched for age ( $\pm 5$  years) and gender will be recruited for study participation.

**Participant Recruitment:** Patients referred by their physician following routine physical examinations will be approached for potential study enrollment. Physicians will be informed of the inclusion and exclusion criteria and will be able to assure us that the patient is an appropriate study participant and that he/she is willing to speak with the study coordinators.

1. Veterans with SCI responding to IRB-approved articles in lay publications and advertisements.
2. Veterans with an ongoing relationship with our center (Metabolic, Pulmonary, or GI SCI clinics).

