**Exclusion Criteria:**

1. known cardiovascular, kidney or untreated thyroid disease
2. traumatic brain injury (mod-severe)
3. diabetes mellitus
4. acute illness or infection
5. broken, inflamed, or otherwise fragile skin
6. pregnancy
7. BMI  $>30 \text{ kg/m}^2$
8. smoking

**Methods:** On 3 separate days (Phases 1 & 2), participants will arrive in the laboratory between 8:00-11:00 AM.

**Preparation for Study Visits:** Participants will be instructed to avoid caffeine and alcohol, maintain normal salt and water intake, and avoid strenuous exercise for 24 hours prior to study on each visit. Participants will wear a T-shirt and shorts during all visits to maximize skin exposure to the warm temperature. The T-shirt will also prevent the cooling vest from directly touching the skin. Each participant will be instructed to eat a light meal (plain bagel or 2 pieces of toast) 2 hours prior to their visit. Participants will be asked to empty their bladders prior to the study visit and again upon arrival, if necessary.

**Instrumentation:** (*For all participants*) After obtaining informed consent, participants will be instrumented in a thermoneutral room ( $25^{\circ}\text{C}$ ) and in their wheelchair (Hi-SCI) or a provided wheelchair for AB controls. Participants will remain seated and relatively still but will be instructed to use their pressure relief seat cushion (e.g., Roho) and maintain their usual pressure relief schedule (e.g., weight shifting every 15 minutes). Laser Doppler flowmetry (LDF) will be used to measure changes in microvascular perfusion rate by placing a Doppler probe on the skin of the ventral forearm and calf bilaterally as an index of vascular sympathetic withdrawal. Changes in skin blood flow will be assessed from calculations of cutaneous vascular conductance (CVC = LDF/MAP), a more accurate measure of change in skin blood flow. An automated blood pressure cuff will be placed above the elbow to measure brachial blood pressure (BP) and heart rate (HR). Sweat rate (SR) will be measured by the Quantitative Sweat Measurement System (WR Medical Electronics, Stillwater, MN) with capsules secured to 4 sites: left

upper arm, left forearm, left mid-thigh, and left midcalf (C5, T1, L3, and L5 dermatomes, respectively). A pulse oximeter will be placed on the second digit to detect blood oxygen saturation. An infrared ear thermometer will be used to assess tympanic temperature.

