**2. Thermal Challenge with Wet Cooling Vest vs. No Vest (Phase 2; 2 visits, participants with Hi-SCI only):** After 15 minutes of baseline data collection in a thermoneutral environment (25°C), participants with HI-SCI will be fitted with an appropriately sized cooling *wet vest* or will wear *no vest* (in random order). To provide evaporative heat loss, the vest material will be saturated with water using a spray bottle. Participants will then be transferred into a warm (35°C, 35% relative humidity) thermal chamber for up to 2 hours. Tcore (Bair Hugger™ Spot On™ forehead skin sensor ) and Tsk (thermocouples at multiple sites under the vest and on hands and feet) will be measured continuously; subjective TS and TC will be measured at 10-minute intervals; LDF will be measured as above (for CVC) at 20-minute intervals. SR will be measured for 15 minutes every 30 minutes (4 times). HR, BP, blood oxygen saturation, and tympanic temperature will be measured at 10-minute intervals for vital signs' information. Participants will be queried if they have any feelings of discomfort. If the participant's Tsk underneath the vest falls below 20°C, or Tcore rises to 38°C, and/or the participant requests study termination because of discomfort, the vest will be removed, the heat challenge will be immediately terminated, and the participant will be transferred to a cool environment, covered with cool blankets, as appropriate, and provided cold liquids. The study physician will be directly responsible for subjects' medical safety during study protocols. Subjects' Tcore, HR and BP, will be monitored at frequent intervals. Symptoms suggestive of AD or hyperthermia will be assessed every 10 minutes. The study physician will be notified immediately of any symptoms or signs of concern. Subjects will be medically evaluated promptly, and the study terminated if any safety issues arise. Subjects will be monitored for at least 30 minutes of recovery to ensure Tcore returns to within 1% of BL value.

**Determinants of Efficacy Failure or Success for Phase 2:** 65% of participants in the *wet vest* condition will have a significantly reduced elevation in Tcore ( $\leq 0.3^{\circ}\text{C}$ ), and 2) a greater percentage will report increased thermal comfort (decreased perception of feeling “hot”, “very hot”, or “uncomfortable”) compared to the expected increase in Tcore of  $0.6^{\circ}\text{C}$  and reported thermal comfort in the *no vest* condition.

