**Sample Size and Statistical Approach:** We are hypothesizing that after 2 hours of heat exposure, the average increase in Tcore of persons with Hi-SCI with the wet cooling vest will be  $0.3 \pm 0.3^{\circ}\text{C}$  compared to an increase of  $0.6 \pm 0.3^{\circ}\text{C}$  (data from our prior study using an identical heat challenge, but with no vest). Therefore, a sample size of 10 participants would be needed to achieve a power of 81% for a two-sided, one-sample analysis at an alpha of 0.05. For Phase I (safety), descriptive statistics will be used to determine the number of participants who have a vest failure. Vest failure will be defined as any area of skin under the vest (Tsk) with a temperature  $<20^{\circ}\text{C}$  and/or the number of participants who report a TS of “cold” or “very cold”. For efficacy testing, a 2 x 2 (condition, time) repeated measures ANOVA will be used to determine significant main or interaction effects. If main or interaction effects are determined, post hoc analysis will be performed using t-tests or appropriate non-parametric tests to determine significant differences between conditions. Significance will be set at an alpha level of 0.05.

3a. Basic Information - Even if described under “Procedures”, list the following information, where pertinent:

3a. i) Procedures to be used (e.g., biopsy, surgical operation, interview, experimental diet, infusion, drug administration, etc.) and with what frequency?

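### Phase 2 is a two-visit crossover in 10 participants, but the plan does not say that condition order is balanced and its ANOVA has no visit (period) term

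*Combined protocol and SAP*

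**What the plan says.** Section 3, Research Design, describes Phase 2 as a single-group repeated measures comparison of wet vest and no vest, "administered in random order". The Phase 2 thermal challenge paragraph repeats that the conditions come "in random order" and gives the schedule as "2 visits, participants with Hi-SCI only". Neither place states a randomisation method, a block or an equal split, and neither rules one out.

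On timing, Methods says: "On 3 separate days (Phases 1 & 2), participants will arrive in the laboratory between 8:00-11:00 AM". It sets no minimum or maximum interval between the two Phase 2 visits.

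For efficacy, Sample Size and Statistical Approach says that "a 2 x 2 (condition, time) repeated measures ANOVA will be used to determine significant main or interaction effects", and that if effects are found "post hoc analysis will be performed using t-tests or appropriate non-parametric tests to determine significant differences between conditions". No visit, period or sequence term is named. The same paragraph states that "a sample size of 10 participants would be needed to achieve a power of 81% for a two-sided, one-sample analysis", for a mean rise of 0.3 (SD 0.3)°C with the vest against 0.6 (SD 0.3)°C without.

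**The concern.** A participant's second two-hour session in the chamber may differ from the first, for example through familiarity or earlier heat exposure. In a crossover such a shift is removed by balancing the orders and fitting a period term. The plan commits to neither.

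The time factor in the ANOVA cannot do this job. Each participant meets each condition at one visit only, so time crossed with condition must mean time within a session, such as baseline against the end of heat exposure.

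At stake is either part of a visit effect being read as a vest effect, if the orders are uneven, or lost power, if they are even. The stated power of 81% leaves little to spare.

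**Working it through.** **Inputs from the plan:** N = 10; planned difference 0.6 − 0.3 = 0.3°C; SD 0.3°C; two-sided alpha 0.05; stated power 81%.

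**Assumptions not in the documents:** a visit shift π (second visit minus first, common to all participants) of 0.1, 0.2 or 0.3°C, and a within-person difference SD of 0.3°C. The plan's own calculation implies that SD. With SD 0.3 in each condition it corresponds to a correlation of 0.5, since 2 × 0.09 × (1 − 0.5) = 0.09.

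**Step 1: the plan's figure.** A one-sample t-test with 9 df and noncentrality √10 × 0.3/0.3 = 3.16 has power 80.3%. This reproduces the stated 81% to within a point. With two time levels, the condition-by-time test is equivalent to this paired test on the rise.

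**Step 2: effect on the estimate.** Let d be the no-vest rise minus the vest rise, and τ the vest effect. Vest-first participants have expected d = τ + π; no-vest-first participants have τ − π. With n1 and n2 in the two orders, the mean of d is τ + π(n1 − n2)/10.

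| Split | Share of π in estimate | Bias, π = 0.1 / 0.2 / 0.3°C |
|---|---|---|
| 5:5 | 0% | 0 / 0 / 0 |
| 6:4 | 20% | 0.02 / 0.04 / 0.06 |
| 7:3 | 40% | 0.04 / 0.08 / 0.12 |
| 8:2 | 60% | 0.06 / 0.12 / 0.18 |

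The sign depends on which order is the more frequent. By simulation (100,000 replicates per setting), type I error of the unadjusted test is 5.5%, 6.4% and 6.4% at 7:3, and 7.6%, 13.9% and 20.0% at 8:2.

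**Step 3: how likely is an uneven split?** If order were simply randomised, the binomial (10, 0.5) gives 5:5 with probability 24.6%, 7:3 or worse 34.4%, and 8:2 or worse 10.9%.

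**Step 4: effect on power at 5:5 without a period term.** The bias is zero, but the expected variance of d becomes 0.09 + π² × 10/9, that is 0.101, 0.134 and 0.190. The SD is then 0.32, 0.37 and 0.44°C instead of 0.30. Simulated power is 77%, 66% and 48%.

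**Step 5: with a period term.** The estimate is the average of the two order means, with SE = (0.3/2) × √(1/n1 + 1/n2) on 8 df. Power no longer depends on π:
- 5:5: SE 0.0949, power 79.1%
- 6:4: SE 0.0968, power 77.4%
- 7:3: SE 0.1035, power 71.9%
- 8:2: SE 0.1186, power 60.3%

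The period term removes the bias at any of these splits, but power close to the planned level also needs the balance.

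**The case against.** The plan is silent on the method of randomisation. Silence is not a decision to leave order unbalanced, and the probabilities in Step 3 apply only if randomisation is simple. That stands.

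Even under simple randomisation there is no systematic bias. Averaged over all splits the estimate is unbiased and type I error is 5.0% to 5.2% for the three assumed shifts. The bias exists only given the split obtained. A 5:5 or 6:4 split has probability 24.6% + 41.0% = 65.6%. With a 0.1°C shift the average absolute bias is 0.246 × 0.1 = 0.025°C, about a quarter of the standard error of 0.3/√10 = 0.095°C. That stands too. However, the trial will be run once, and averaging does not recover the power: under simple randomisation the unadjusted test has 76%, 64% and 50%.

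The sessions are also well standardised. Chamber temperature and humidity, arrival window, clothing, meal and pre-visit restrictions are fixed, and the endpoint is a rise from a baseline taken at each visit. This makes a large visit effect less likely but does not exclude one, and the material losses do need shifts of 0.2 to 0.3°C.

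Finally, this is an exploratory pilot, and its declared success rule is a proportion of wet-vest participants, which a period term does not alter. That lowers the weight of the point. It does not make the stated ANOVA suitable for a two-visit crossover.

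**Conclusion.** The point holds as a modest weakness with a cheap remedy. Balance of order is not stated, and the stated model has no visit term. Any visit effect common to participants therefore enters the vest estimate in part if the split is unequal, or stays wholly in the error if it is equal. At 7:3 the bias is 0.04 to 0.12°C on a planned 0.3°C; at 5:5 power falls to between 77% and 48%. These sizes rest on assumed shifts of 0.1 to 0.3°C and a within-person difference SD of 0.3°C. If there is no visit effect, nothing is lost.

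A reader might infer three stronger things that the documents do not support:
- That order is randomised without balance: the method is simply not given.
- That every visit effect contaminates the vest estimate: at 5:5 a common shift cancels from it.
- That calendar season is the threat and a visit term would cure it: no schedule is given, and under staggered recruitment some participants would move into warmer weather and others out of it, which a common visit term does not remove.

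**What to change.** Two changes to the text:
- In Research Design, state that condition order comes from a concealed list fixed at five vest-first and five no-vest-first.
- In Sample Size and Statistical Approach, add visit (period) as a fixed effect in the Phase 2 core temperature model, and carry the same adjustment into the follow-up comparison of conditions. If a non-parametric test is used there, compare the visit 2 minus visit 1 differences between the two orders with a rank-sum test.

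No extra participants are needed. The cost is one degree of freedom (critical t from 2.26 to 2.31). At 5:5, power is 79.1% whatever the size of a common additive visit effect, against 80.3% for the planned test when there is none. The change does not deal with season under staggered recruitment and leaves the 65% success rule as it is.
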